2. Objectives (include all primary and secondary objectives)

Primary objective:

To evaluate the effectiveness of Prevena Peel & Place Dressing using the standard KCI VAC after suture closure versus standard closure at reducing wound infections in patients undergoing pancreaticoduodenectomy

Secondary objective:

To evaluate the impact of Prevena Peel & Place Dressing using the standard KCI VAC after suture on hospital length of stay, readmission, and time to adjuvant therapy

3. Background (briefly describe pre-clinical and clinical data, current experience with procedures, drug or device, and any other relevant information to justify the research)

Although pancreaticoduodenectomy (PD) outcomes have improved, it remains a procedure with a high perioperative complication rate. Surgical site infection (SSI) is one of the most common complications after PD. In a retrospective review of all patients who underwent PD at Johns Hopkins between 9/2011-8/2014, a total of 679 patients, 30-day SSI was observed in 16.7%. By univariate analysis, perioperative blood transfusion, operative time greater than 7 hours, pre-operative chemotherapy and/or radiation, bile stent, absence of a superficial wound vacuum closure device, and vascular resection were associated with SSI (all, $p < 0.05$). On multivariable analysis, pre-operative bile stent/drain and neoadjuvant chemotherapy were independent predictors of SSI (all, $p < 0.001$). Studies in colorectal patients have found an estimated cost of up to \$1400 per patient secondary to prolonged hospitalization, wound care, and wound complications in patients with procedures complicated by a SSI. Furthermore, in another study of 1144 patients undergoing PD between 1995 and 2011 at Johns Hopkins Hospital, post-operative complications delayed time to adjuvant therapy, decreased median survival.¹

Our hypothesis is that placement of Prevena Peel & Place Dressing using the standard KCI VAC after suture on patients undergoing PD at highest risk of infection will result in a significant decrease in SSI rate. We plan to perform a randomized control trial where patients who have had pre-operative bile stent/drain placement and/or neoadjuvant chemotherapy will undergo closure with Prevena Peel & Place Dressing using the standard KCI VAC after suture versus standard closure. We will then follow these patients for 30 days post-operatively to determine SSI and other peri-operative complication rate.

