Our institution has extensive experience with using this product for the prevention of SSI in patients undergoing surgery over the past several years, most specifically after ventral hernia repair. Superficial wound vacuum closure has been shown in a previous study by our group to decrease SSI from 32% to 9% ($p < 0.001$) and surgical site occurrence (SSO) from 42% to 17% ($p < 0.001$) in patients undergoing ventral hernia repair. Furthermore, when used in grade 3 ventral hernias, superficial wound vacuum closure had an SSI rate of 5.2% and an SSO of 20.7% at 90 days, which is lower than previously published rates using standard closure in these complex hernia repairs. All surgeons who will participate in this study have familiarity with the use of the wound vacuum device after surgical closure.

4. Study Procedures

- a. Study design, including the sequence and timing of study procedures (distinguish research procedures from those that are part of routine care).

All patients who are planned to undergo pancreaticoduodenectomy at Johns Hopkins Hospital will be assessed for eligibility and enrolled. Members of the department of surgery who are listed as the team members will be responsible for approaching the participants. Patients will be screened for eligibility. Only patients who have received neoadjuvant therapy and/or have undergone biliary stent placement will be approached. In addition patients will also be screened for known allergies to silver or acrylic adhesives.

Date: April 10, 2018

Principal Investigator: [name]

Application Number: IRB00109564

Recruitment will take place in the (i) surgical clinics, or (ii) at the pre-operative evaluation clinics prior to the surgery. Recruitment process will be mindful of patient privacy issues.

Discussions will be held by the potential participant's clinical and will not likely involve any additional patient protected health information beyond what is already required for the standard medical care. A written consent will be taken from these patients. The patients who are suitable candidates for the study will be approached in a clinical setting that is surgical clinics, preoperative assessment clinics, etc.

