Those members of the research team (principal investigator, co-investigator, research nurse) who consent patients have been trained in informed consent procedures, are familiar with the protocol, and are listed as a consentor in the application document. Patients are given adequate time and privacy to consider the research study. Before the patient signs the consent, the consentor must be satisfied that the participant understands the information provided, has had an opportunity to discuss the information and ask questions, and is aware that he/she may withdraw from the study at any time.

A copy of the signed consent form will be provided to the patients at time of consent. Contact information will be provided to these patients so that they can contact the study team in the future, if they have any questions regarding the study.

Once consented, these patients will be entered into CRMS.

All consented patients will undergo the same standard PD. At the time of closure the patients will be randomized to either standard closure or closure using the Prevena Peel & Place Dressing using the standard KCI VAC after suture closure.

The device will be left in place for 4 days after surgery. As part of the patients' clinical evaluation the surgical wound site will be inspected daily by the surgical team. If there are signs of infections the device will be removed. All patients will have their device removed prior to discharge.

The patients will be evaluated for wound infection during their hospital stay and also during their outpatient follow-up for up to 30 days after surgery. The CDC guidelines will be used to diagnose SSIs.

All patients will be followed for 30 days to collect data on SSI and other post-operative complications.

In total we plan to consent 144 patients for this study – 72 patients in the Prevena Peel & Place Dressing using the standard KCI VAC after suture closure arm, and 72 patients in the standard control arm.

b. Study duration and number of study visits required of research participants.

The study duration will be approximately 2 years. The patients will not require additional research visits.

5. Inclusion/Exclusion Criteria

Inclusion Criteria:

1. Patient to undergo pancreaticoduodenectomy for a pancreatic tumor at the Johns Hopkins Hospital
2. Patient treated with neoadjuvant chemotherapy with or without radiation therapy prior to surgical resection, AND/OR placement of a biliary stent and/or drain for biliary tree decompression

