Exclusion Criteria:

1. Age 18 years or younger
3. Laparoscopic or robotic pancreaticoduodenectomy
4. Patient did not undergo either placement of a preoperative biliary stent/drain or neoadjuvant chemotherapy with or without radiation therapy.
5. All patients who are have known allergies or are sensitive to silver and acrylic adhesives.

6. Drugs/ Substances/ Devices

- a. The rationale for choosing the drug and dose or for choosing the device to be used.
Our institution has extensive experience with using this product for the prevention of SSI in patients undergoing surgery over the past several years, most specifically after ventral hernia repair. Superficial wound vacuum closure has been shown in a previous study by our group to decrease SSI from 32% to 9% ($p < 0.001$) and surgical site occurrence (SSO) from 42% to 17% ($p < 0.001$) in patients undergoing ventral hernia repair. Furthermore, when used in grade 3 ventral hernias, superficial wound vacuum closure had an SSI rate of 5.2% and an SSO of 20.7% at 90 days, which is lower than previously published rates using standard closure in these complex hernia repairs.

7. Study Statistics

- a. Primary outcome variable.
The primary outcome variable is surgical site infection (SSI) rate
- b. Secondary outcome variables.
The secondary outcome variables are hospital length of stay, readmission rate, and time to adjuvant chemotherapy
- c. Statistical plan including sample size justification and interim data analysis.
The primary outcome variable, SSI rate, will be analyzed using a chi-square test. The secondary outcome variable of hospital length of stay will be analyzed using a t-test if the data are normally distributed or a ranksum test if they are not. The secondary outcome variable of readmission rate will be analyzed using a chi-square test. The secondary outcome variable of time to adjuvant chemotherapy will be analyzed using survival analysis methods, including Kaplan-Meier curves and log-rank test.

Prior data from our institution has demonstrated that the risk of a surgical site infection after pancreaticoduodenectomy is 30% if the patient either underwent neoadjuvant chemotherapy or had a biliary stent/drain placed before surgery. This study has been powered to show a decrease in SSI rate from 30% to 10%, and thus would necessitate 72 patients in each arm of the trial (Open Epi software, with Fleiss continuity correction).

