Interim data analysis will only performed to monitor for futility, as described below.

Date: April 10, 2018

Principal Investigator: [name]

Application Number: IRB00109564

d. Early stopping rules.

We will perform an interim analysis when SSI results are available for the first 36 patients in each group. Conditional power calculations will be performed according to the method proposed by Proschan, Lan, and Wittes (2006), assuming that the results seen up until the interim analysis continue until the end of the trial (empirical conditional power). If the conditional power under the empirical assumption is less than 0.50, the trial will be terminated for futility.

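### Does the plan lose precision by testing SSI with a plain chi-square instead of stratifying by stent/drain and neoadjuvant status?

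*Combined protocol and SAP*

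**What the plan says.** The primary endpoint is a binary infection outcome (section 7a: "The primary outcome variable is surgical site infection (SSI) rate"), followed to 30 days. Section 7c gives the test in one sentence: "The primary outcome variable, SSI rate, will be analyzed using a chi-square test". It sizes the trial at 72 per arm for 30% versus 10%, using the Fleiss continuity correction.

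On allocation, section 4a gives the timing and the two arms ("At the time of closure the patients will be randomized to either standard closure" or the vacuum dressing). It does not mention sequence generation, blocking or stratification.

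On risk factors, section 3 reports from the 679-patient series: "On multivariable analysis, pre-operative bile stent/drain and neoadjuvant chemotherapy were independent predictors of SSI". Both factors define eligibility. Section 4a says: "Only patients who have received neoadjuvant therapy and/or have undergone biliary stent placement will be approached". Section 5 excludes anyone matching this description: "Patient did not undergo either placement of a preoperative biliary stent/drain or neoadjuvant chemotherapy with or without radiation therapy".

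Section 7d sets one look at 36 per arm: "If the conditional power under the empirical assumption is less than 0.50, the trial will be terminated for futility".

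**The concern.** The investigators name two prognostic factors, select patients on them, record both before randomization, and then use neither in the stated allocation or analysis. Because a patient qualifies with either factor or both, the trial mixes stent/drain-only, neoadjuvant-only and both-factor patients. With 72 per arm, chance could put more both-factor patients in one arm. The plan would then have no prespecified adjusted result, and any adjustment would be post hoc. The interim look has half the patients and can end the trial, so it is more exposed still. A stratified test needs no new data, so omitting it looks like free precision given away.

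**Working it through.** **1. The plan's own figure.** Inputs from section 7c: 30% versus 10%, Fleiss correction. Two-sided 5% and 80% power are not stated and are assumed.

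n = [1.96·√(2·0.2·0.8) + 0.842·√(0.3·0.7 + 0.1·0.9)]² / 0.2² = (1.109 + 0.461)² / 0.04 = 61.6

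With the correction: (61.6/4)·[1 + √(1 + 4/(61.6·0.2))]² = 71.2, rounded up to **72**. The stated size reproduces.

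**2. Validity.** In simulation under simple randomization, null rejection is 4.9-5.2% for both the chi-square and the CMH test. If the list were in fact stratified, the plain chi-square would be slightly conservative: 4.8-4.9% at a both-versus-one odds ratio (OR) of 2 and 4.3-4.6% at OR 3. Neither case inflates the error rate. Nor does the conservatism cost power: at OR 3 with group shares 25/50/25, chi-square power is 87.8% with a stratified list and 87.4% with simple randomization.

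**3. What is left to adjust for.** The predictor result comes from all 679 patients, including those with neither factor, whom the trial excludes. Suppose the 16.7% overall rate and the 30% rate with a factor describe one series, and a share q had a factor (assumed 30% to 50%). The neither-factor rate is then (16.7 - 30q)/(1 - q):
- q = 0.3: 7.7/0.7 = 11.0%
- q = 0.5: 1.7/0.5 = 3.4%

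Under these assumptions, part of the reported contrast is against patients who cannot enrol. What remains is the contrast between both factors and one, and between the two single factors. The documents give no figure for either.

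**4. Chance imbalance.** Taking the difference of two Binomial(72, p) counts, the arms differ by more than 10 points in both-factor share with probability 11.7%, 18.5% or 21.1% for p = 20%, one third or 50% (assumed). For equal thirds, a 10-point imbalance has this effect:
- OR 2: control risks 25.0% and 40.0%, device 7.8% and 14.4%. The mean gap is (15.0 + 6.6)/2 = 10.8, so the shift is 1.1 points.
- OR 3: control 22.0% and 45.9%, device 6.4% and 17.1%. The mean gap is (23.9 + 10.7)/2 = 17.3, so the shift is 1.7 points.

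Across the mixes examined the shift is 1.0 to 1.9 points. The standard error of the risk difference is √(0.21/72 + 0.09/72) = 6.5 points, so the shift is under a third of one standard error. Under simple randomization the chi-square's variance already allows for such imbalance.

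**5. Power with the interim rule.** At information fraction 0.5, empirical conditional power is Φ[(Z/√0.5 - 1.96)/√0.5]. It is below 0.50 exactly when Z < 1.96·√0.5 = 1.386. Simulation: 100,000 trials per scenario; marginal rates fixed at 30% and 10%; shares (stent/drain only, neoadjuvant only, both) 50/20/30, equal thirds, 40/10/50 and 60/20/20. In the last two columns of the table, success means passing the interim and reaching two-sided 5% at the end. The chi-square with simple randomization gives about 87% at the final test alone and about 75% with the interim.

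| OR, both vs one | CMH minus chi-square, simple randomization, final test only | Same, with interim | CMH with stratified list minus chi-square with simple randomization, with interim |
|---|---|---|---|
| 1 | -0.8 to -0.9 | -1.7 to -1.8 | -0.7 to -0.9 |
| 2 | -0.2 to -0.5 | -0.8 to -1.2 | -0.4 to +0.1 |
| 3 | +0.3 to +0.7 | -0.4 to +0.3 | +0.8 to +1.2 |

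Entries are percentage points. The last column compares separate simulations and carries error of a few tenths. Stratifying costs a little when the strata carry little information, and the cost is larger at 36 per arm. In the 40/10/50 mix the smallest stratum has 36·0.10 = 3.6 patients per arm at the interim.

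**The case for a change.** The strongest case for stratifying rests on robustness. At 36 per arm, a gap of more than 10 points in both-factor share has probability 30%, 38% or 41% for the three shares in step 4, and at OR 2 to 3 the two tests disagree on stopping in about 4.4% to 5.7% of trials at the design effect. Fixing an adjusted statistic in advance would settle which one counts. But the plan already fixes one, the chi-square. The disagreement also does not favour CMH, which stops an effective device in 20.5-21.7% of trials against 20.1-20.6%.

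A larger gain is possible if the factors are strong. At OR 4, with the interim included, CMH gains 0.8 to 1.4 points under simple randomization and 1.8 to 2.5 with a stratified list. If the two single-factor groups also differ from each other (OR 2 to 3 between adjacent groups), a stratified list with CMH gains about 1 to 3 points on the final test alone. That is correct arithmetic on assumed strengths. The reported p < 0.001 in 679 patients suggests an odds ratio of roughly 2 or more per factor (prevalence assumed), but in the whole series, not between the groups enrolled here. Most of the gain also needs a stratified list, and the documents do not show whether allocation has begun.

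Two modest points stand. Section 4a could say how the list is generated, and an adjusted sensitivity analysis would be reasonable. Neither makes the primary analysis wrong.

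**Conclusion.** The concern does not hold. The unadjusted chi-square is a valid prespecified test, the sample size reproduces, and the known predictors are already used to select a high-risk population. Changing only the test, with the futility rule included, moves the chance of success by between -1.8 and +0.3 points over odds ratios of 1 to 3. Pairing it with a stratified list gives -0.9 to +1.2. Plausible chance imbalance moves the estimate by 1 to 2 points against a 20-point effect. These figures assume two-sided 5% testing, no dropout, and the risk-group shares and odds ratios listed, none of which the documents supply. On that footing the choice between the two tests is a trade-off of about a point either way, and the sponsor may reasonably keep the simpler one.

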TITLE: Comparison Between Wound Vacuum Dressing and Standard Closure to Reduce Rates of Surgical Site Infections

NCT: NCT03021668

PI: [name]

DATE: 04/10/2018

JHM IRB - eForm A – Protocol

- Use the section headings to write the JHM IRB eForm A, inserting the appropriate material in each. If a section is not applicable, leave heading in and insert N/A.
- When submitting JHM IRB eForm A (new or revised), enter the date submitted to the field at the top of JHM IRB eForm A.

1. Abstract

- a. Provide no more than a one page research abstract briefly stating the problem, the research hypothesis, and the importance of the research.

Although pancreaticoduodenectomy (PD) outcomes have improved, it remains a procedure with a high perioperative complication rate. Surgical site infection (SSI) is one of the most common complications after PD. In a retrospective review of all patients who underwent PD at Johns Hopkins between 9/2011-8/2014, a total of 679 patients, 30-day SSI was observed in 16.7%. By univariate analysis, perioperative blood transfusion, operative time greater than 7 hours, pre-operative chemotherapy and/or radiation, bile stent, absence of a superficial wound vacuum closure device, and vascular resection were associated with SSI (all, $p < 0.05$). On multivariable analysis, pre-operative bile stent/drain and neoadjuvant chemotherapy were independent predictors of SSI (all, $p < 0.001$). Studies in colorectal patients have found an estimated cost of up to \$1400 per patient secondary to prolonged hospitalization, wound care, and wound complications in patients with procedures complicated by a SSI. Furthermore, in another study of 1144 patients undergoing PD between 1995 and 2011 at Johns Hopkins Hospital, post-operative complications delayed time to adjuvant therapy, decreased median survival.¹

Our hypothesis is that placement of Prevena Peel & Place Dressing using the standard KCI VAC after suture on patients undergoing PD at highest risk of infection will result in a significant decrease in SSI rate. We plan to perform a randomized control trial where patients who have had pre-operative bile stent/drain placement and/or neoadjuvant chemotherapy will undergo closure with Prevena Peel & Place Dressing using the standard KCI VAC after suture versus standard closure. We will then follow these patients for 30 days post-operatively to determine SSI and other peri-operative complication rate.

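### Does time to adjuvant chemotherapy need a stated cut-off, censoring date and death rule before its log-rank test can be used?

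*Combined protocol and SAP*

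**What the plan says.** The secondary objective in section 2 is to assess the dressing's impact "on hospital length of stay, readmission, and time to adjuvant therapy". Section 7b lists the outcomes: "The secondary outcome variables are hospital length of stay, readmission rate, and time to adjuvant chemotherapy". Section 7c gives the analysis: "The secondary outcome variable of time to adjuvant chemotherapy will be analyzed using survival analysis methods, including Kaplan-Meier curves and log-rank test".

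Three other places bear on the point:

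- **Follow-up.** Section 4a says "All patients will be followed for 30 days to collect data on SSI and other post-operative complications". Section 4b adds "The patients will not require additional research visits" and puts the whole study at about 2 years, without making that a censoring date.
- **Eligibility.** Section 5 admits a "Patient to undergo pancreaticoduodenectomy for a pancreatic tumor at the Johns Hopkins Hospital" who also had neoadjuvant treatment, a biliary stent or drain, or both. Planned adjuvant chemotherapy is not required.
- **Motivation.** The abstract cites an institutional series in which "post-operative complications delayed time to adjuvant therapy, decreased median survival".

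**The concern.** Kaplan-Meier and log-rank methods use a censoring time but do not define it. Because planned adjuvant treatment is not an entry condition, some patients may never start. If they stay at risk to a common cut-off, the curve levels off at the true share started. If they leave early while later starts are still counted, the curve climbs towards 100% and the test compares timing among starters. These are different questions, and the same patients could give different answers. Leaving the rule open also allows it to be chosen after the results are seen.

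Two smaller points add to this. Deaths before starting are not mentioned, and censoring them overstates the share started. The objective and the outcome also use different terms. Section 5 refers to "Patient treated with neoadjuvant chemotherapy with or without radiation therapy prior to surgical resection", so the protocol does distinguish chemotherapy from radiation, and a patient whose first adjuvant treatment was radiation would count under one term only.

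**Working it through.** **The plan's own figure.** No number is stated for this outcome. The only sample-size figure, 72 per arm, concerns SSI at 30% against 10%. It reproduces exactly with the Fleiss continuity correction if a two-sided 5% level and 80% power are assumed (the protocol states neither). It does not depend on this outcome.

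**Censoring of non-starters.** From the protocol: 72 per arm. Assumed: lognormal start times with (median, log-SD) of (42, 0.45), (56, 0.35) or (70, 0.25) days; 70% starting unless stated; records complete to day 180; no deaths; two-sided 5% log-rank test. Ranges run over the three start-time settings. Rule A keeps non-starters at risk to day 180. Rule B censors all of them at day 30 but still counts starts to day 180.

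| Assumed truth | Significant, A | Significant, B | Verdicts differ |
|---|---|---|---|
| No effect | 4.7% to 5.3% | 5.3% to 5.6% | 9% to 10% |
| Share starting 60% vs 80% | about 70% | 5% to 7% | 66% to 69% |
| Timing only, HR 2.0 | 18% to 19% | 91% to 92% | 73% to 76% |
| Effect only through SSI, 30% vs 10% | 5% to 23% | 5% to 42% | 11% to 40% |

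Both rules hold the error rate at about 5%, so neither is invalid.

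**How far this depends on rule B.** Rule B lets the censoring date depend on what happens later: a patient leaves at day 30 only if no start is ever recorded. Records searched to day 180 for starts would normally also show who had not started by then. Replace day 30 with a last contact spread uniformly over days 30 to 180 (also an assumption) and compare with rule A again:

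| Assumed truth | Verdicts differ, rule B | Last contact days 30 to 180 |
|---|---|---|
| No effect | 9% to 10% | 2% to 5% |
| Share starting 60% vs 80% | 66% to 69% | 8% to 17% |
| Timing only, HR 2.0 | 73% to 76% | 5% to 11% |
| Effect only through SSI | 11% to 40% | 2% to 10% |

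Repeat runs put the middle two rows together at about 5% to 19%. With last contact spread over days 90 to 180, disagreement is under 3%.

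**How informative the outcome is.** By Schoenfeld's formula, if 70% of 144 patients start (101 events), power for an assumed hazard ratio of 1.5 is about 53%. With 10% starting by the cut-off (14 events) it is about 12%. All three assumed medians lie beyond day 30, so a 30-day window applied to everyone would leave few events.

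**Deaths.** If a share d dies before anyone starts and is censored, a true share p reads as p/(1 − d). With p = 0.70, d = 0.02 gives 0.70/0.98 = 0.714 and d = 0.08 gives 0.70/0.92 = 0.761. This is an upper bound, since later deaths bias less. Under assumed constant daily hazards of 0.012 for starting and 0.001 or 0.003 for death, the 90-day share is:

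- deaths censored: 1 − exp(−0.012 × 90) = 66.0%
- cumulative incidence, death hazard 0.001: (0.012/0.013) × [1 − exp(−0.013 × 90)] = 63.7%
- cumulative incidence, death hazard 0.003: (0.012/0.015) × [1 − exp(−0.015 × 90)] = 59.3%

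The shift is about 2 to 7 points in the level of a curve. No shift in the comparison between arms was shown, and the protocol gives no mortality figure.

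**The event.** Sections 7b and 7c, which govern the analysis, both say chemotherapy. The broader word appears in the objective and the background. Section 4a uses the same shorthand before surgery: it screens for neoadjuvant therapy where the section 5 criterion is neoadjuvant chemotherapy with or without radiation. That criterion adds radiation to chemotherapy and does not describe radiation alone.

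**The case for a change.** The strongest case for a change is that the silence is real. No section gives the cut-off, the non-starter rule or the death rule. Day 30 is the only per-patient follow-up stated and there are no research visits, so censoring non-starters there cannot be ruled out from the text. Delayed adjuvant therapy is part of the trial's rationale, and a few sentences would close the gap.

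The omission stands, and so does the point that a rule fixed in advance guards against choosing one later. The claim of a large effect does not stand. It needs the day-30 rule, although the 30-day sentence concerns SSI and complications and sets no window here. It also needs effect sizes with no source in the documents. The one route the protocol suggests is fewer complications and hence less delay, and on that route both rules are weak and disagree in only 2% to 10% of trials under spread-out last contact.

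Nor is there one correct wording to insert. Keeping non-starters at risk to a common cut-off favours the question of how many start and cuts power for a pure timing effect to 18% to 19%. Timing among starters is a question the investigators could legitimately prefer, though it compares groups selected after randomization. Collecting start dates for patients treated elsewhere could also take more than wording.

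**Conclusion.** The plan leaves out detail here, but no rule it states is wrong. Censoring at the date last known not to have started is the ordinary way to carry out a Kaplan-Meier analysis. Under it, the choice of date changes the log-rank verdict in about 5% to 19% of trials with last contact spread over days 30 to 180, and in under 3% over days 90 to 180, even with the large assumed effects. The 66% to 76% figure is a worst case tied to one unlikely rule. Censored deaths shift the share started by a few points under assumed mortality, with no demonstrated effect on the comparison. The two names for the event are plausibly shorthand, and the outcome list and analysis sentence agree.

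These sizes rest on assumed start times, shares, effects and contact dates. The outcome is secondary and unpowered, and the SSI analysis, the 72 per arm and the futility rule do not depend on it. No change to the plan follows.

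### The futility rule in section 7d would stop about one in five trials in which the dressing works as planned, and 72 per arm then has about 75% power or less

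*Combined protocol and SAP*

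**What the plan says.** Section 7c sizes the trial to detect a fall in SSI from 30% to 10% and concludes that this "thus would necessitate 72 patients in each arm of the trial", giving the method as "Open Epi software, with Fleiss continuity correction". It states neither the significance level nor the target power. On the test it says: "The primary outcome variable, SSI rate, will be analyzed using a chi-square test". It does not say whether that test is continuity-corrected. It limits the interim look to futility.

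Section 7d gives the timing: "We will perform an interim analysis when SSI results are available for the first 36 patients in each group". Conditional power is to be computed on the assumption that the observed trend continues. The consequence is worded as mandatory: "If the conditional power under the empirical assumption is less than 0.50, the trial will be terminated for futility".

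Neither section gives the chance of stopping when the planned effect is real, the power the rule costs, or any sample-size allowance for it.

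**The concern.** A conditional power of 0.50 under the current trend is a demanding hurdle halfway through a trial. An interim estimate from 36 patients per arm is noisy, and the empirical version counts that noise twice: once in the data already seen and again in the projection. A trial running somewhat below its planned effect by chance is then declared futile, although the remaining half of the data could still carry it to significance.

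The primary objective is at stake. A false futility stop ends the trial with a negative message about a dressing that works, and patients not enrolled after the stop cannot be recovered in the analysis. The sample-size statement also promises a power that the plan's own rule removes.

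**Working it through.** **Inputs.** SSI rates 30% and 10%, 72 per arm, Fleiss correction and chi-square test (section 7c). Interim at 36 per arm, empirical conditional power, cut-off 0.50, mandatory stop (section 7d). Two-sided 5% and 80% power are assumptions, tested in step 1.

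**1. Reproduce 72 per arm.** With a mean rate of 0.20:

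- Uncorrected: n = [1.96·√(2·0.2·0.8) + 0.8416·√(0.3·0.7 + 0.1·0.9)]² / 0.2² = 61.6.
- Fleiss-corrected: (61.6/4)·[1 + √(1 + 4/(61.6·0.2))]² = 71.25, rounded up to 72.

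Two-sided 5% with 80% power therefore gives the plan's figure exactly. Other corrected settings do not: one-sided 5% at 80% gives 58, and two-sided 5% gives 80 at 85% power and 92 at 90%. The formula contains no term for an interim look.

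**2. Turn the rule into a boundary.** The information fraction is t = 36/72 = 0.5. Empirical conditional power is

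CP = Φ[(Z₁/√t − 1.96)/√(1 − t)].

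CP < 0.50 is the same as Z₁ < 1.96·√0.5 = 1.386.

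**3. Interim results that would stop the trial.**

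| Standard vs dressing | Rates | Z₁ | CP |
|---|---|---|---|
| 9/36 vs 5/36 | 25.0% vs 13.9% | 1.19 | 0.35 |
| 8/36 vs 4/36 | 22.2% vs 11.1% | 1.26 | 0.40 |
| 12/36 vs 7/36 | 33.3% vs 19.4% | 1.34 | 0.46 |

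For 8/36 vs 4/36 the pooled rate is 12/72 and the standard error is √(2·0.1667·0.8333/36) = 0.0878. So Z₁ = 0.1111/0.0878 = 1.265 and CP = Φ[(1.789 − 1.960)/0.7071] = 0.40.

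**4. Stop probability and power at 30% vs 10%.** All binomial outcomes of both stages (36 + 36 per arm) were enumerated. Power counts significant final results in favour of the dressing.

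| Interim statistic | Final test | P(stop) | Power, no interim | Power with rule |
|---|---|---|---|---|
| Uncorrected | Uncorrected | 20.5% | 87.4% | 75.3% |
| Uncorrected | Corrected | 20.5% | 81.6% | 72.1% |
| CP computed exactly from the binomials | Corrected | 26.8% | 81.6% | 67.6% |
| Corrected | Corrected | 30.5% | 81.6% | 64.8% |

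Normal approximations using the 30%/10% drift at 72 per arm give stop probabilities of 21.0% to 23.1% and power of 72.1% to 74.8%, in line with the first two rows.

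**5. Split the stopped trials.** In the first row, 87.35 − 75.31 = 12.0 percentage points are trials that would have ended significant. The other 20.45 − 12.04 = 8.4 points would have failed anyway. With the corrected final test in the second row the loss is 81.63 − 72.13 = 9.5 points.

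**6. Alternatives at 72 per arm, uncorrected interim statistic.** Under the design alternative the expected final Z is 0.2/√(2·0.2·0.8/72) = 3.0, so CP = Φ[(Z₁·√0.5 + 0.5·3.0 − 1.96)/√0.5]. CP < 0.50 then means Z₁ < 0.46/0.7071 = 0.65.

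| Rule | P(stop), 30% vs 10% | Power, uncorrected final | Power, corrected final | P(stop), 30% vs 30% |
|---|---|---|---|---|
| Empirical CP < 0.50 (plan) | 20.5% | 75.3% | 72.1% | 91.4% |
| Empirical CP < 0.20 | 10.7% | 82.4% | 78.0% | 81.8% |
| Empirical CP < 0.10 | 7.1% | 84.6% | 79.7% | 76.0% |
| Design-alternative CP < 0.50 | 6.4% | 84.9% | 80.0% | 74.0% |

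**The case against.** The strongest reply is that a strict futility rule is a legitimate choice for a single-centre trial. It is pre-specified, it does not inflate the type I error, and it ends 91% of trials early when the dressing does nothing. That stands as far as it goes. A sponsor may pay for early stopping with power, but section 7c should then report the power that is left, and it does not.

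Three further points have some force.

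- **The harm is smaller than the stop rate.** Of the 20.5% stopped, 12.0 points (9.5 with a corrected final test) are lost significant results. This is right: one in five is the chance of a futility verdict on an effective dressing, and the power loss is roughly one in eight to one in ten.
- **The 80% is inferred, and the correction leaves slack.** Both are true. With an uncorrected test, 72 per arm has 87.4% power without an interim look, so 7.4 points of the loss are absorbed and the shortfall against 80% is 80 − 75.3 = 4.7 points. The slack does not cover the loss. A one-sided 5% final test would soften the problem (14.6% stopped, 82.8% power), but that design needs 58 per arm, not 72.
- **The stopped results in step 3 are not near significance.** Their Z values are 1.19 to 1.34 and their differences are 11 to 14 points against a planned 20. They are favourable trends and no more than that. Even so, 8/36 vs 4/36 has the SSI rate halved, and with half the data outstanding it is hard to call futile.

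**Conclusion.** The concern holds. Followed as written, the rule stops 20.5% of trials in which the dressing has exactly the planned effect. It leaves power of 75.3% with an uncorrected chi-square test and 72.1% with a continuity-corrected final test, or 64.8% to 67.6% if the correction also enters the interim calculation. All of these are below the 80% that reproduces 72 per arm, so one in five is the low end of a 20% to 30% range.

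The result rests on two-sided 5% and 80% power, inferred from the exact match to 72, and on the stop being binding, as it is worded. It should be settled before the interim look.

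**What to change.** **Preferred change, section 7d.** Compute conditional power under the design alternative of 30% versus 10% and keep the 0.50 cut-off. Define conditional power as the probability of a final significant result in favour of the dressing. In section 7c, state the significance level, the sidedness, the target power and whether the chi-square test is corrected, and report the stop probability and power under the rule.

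**Second choice.** Keep the empirical assumption and lower the cut-off to between 0.10 and 0.20. This is adequate with an uncorrected test (82.4% to 84.6% power). With a corrected final test it reaches only 78.0% to 79.7%, or 73.4% to 77.0% if the interim statistic is corrected as well.

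**If the present rule is kept.** Either restate the power in section 7c as about 75% (72% with a corrected final test), or enlarge the trial. With the look still at half the data, about 84 per arm restores 80% with an uncorrected test (80.9%), and about 100 per arm if the correction is used throughout (80.4%).

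**Cost.** The preferred change rewrites the conditional-power rule in section 7d and leaves the maximum enrolment at 144. If the dressing has no effect, early stopping falls from 91.4% to 74.0%. A stop saves up to 72 patients, so expected enrolment rises by about 72·(0.914 − 0.740) = 12.5 patients. With the empirical 0.20 cut-off the rise is about 72·(0.914 − 0.818) = 6.9 patients, and with 0.10 it is 72·(0.914 − 0.760) = 11.1.
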